	
 Single dose 660 mg M5717 plus 720 mg pyronaridine (≥ 65 kg) or 540 mg pyronaridine (≥ 45 to < 65 kg) (Cohort 3) 3 doses of Malarone (1,000 mg atovaquone plus 400 mg proguanil hydrochloride [proguanil]) to clear all parasites to measure the natural incidence of infection (Cohort 4) 
Intercurrent Event Strategy:
 
 Intake of rescue medication: composite variable strategy, i.e. endpoint is considered as failure (=positive blood smear at the time of rescue medication intake) Intake of antibiotics or other prohibited medication that impacts treatment effect (e.g. drug with antimalarial activity) at any timepoint: On-treatment strategy, i.e. time to parasitemia is censored at the time of antibiotics or prohibited medication intake Experience of any event that affects absorption (e.g. vomiting within the first 24 hours after dosing): Treatment policy strategy, i.e. treatment effect is estimated regardless of ICE. Death due to malaria: Composite variable strategy, i.e. parasitemia event is assumed at time of death. Death due to other reasons: On-treatment strategy, i.e. time to parasitemia is censored at the time of death 
Population-Level Summary HRs estimated from Cox' Proportional Hazards Model for each dose of M5717 compared to Cohort 4
	
Secondary	
Endpoint: Incidence of parasitemia (positive blood smear).
 
Population: See primary endpoint
 
Treatment: See primary endpoint
 
Intercurrent Event Strategy:
 
 Intake of rescue medication: composite variable strategy, i.e. endpoint is considered as failure (=positive blood smear at the time of rescue medication intake) Intake of antibiotics or other prohibited medication that impacts treatment effect (e.g. drug with antimalarial activity) at any timepoint: On-treatment strategy, i.e. time to parasitemia is censored at the time of antibiotics or prohibited medication intake Experience of any event that affects absorption (i.e. vomiting within the first 24 hours after dosing): Treatment policy strategy, i.e. treatment effect is estimated regardless of ICE Death due to malaria: Composite variable strategy Death due to other reasons: On-treatment strategy, i.e. time to parasitemia is censored at the time of death 
Population-Level Summary: Proportion of participants with parasitemia using Kaplan-Meier estimates for each dose of M5717 and for Cohort 4
	2

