	
Endpoint: Incidence of PCR-adjusted parasitemia (thick smear/microscopy, after adjustment for parasitemia due to new infections as determined by genotyping using PCR techniques).
 
Population: See primary endpoint
 
Treatment: See primary endpoint
	3

Objectives	Estimands/Endpoints	Ref. #
	
Intercurrent Event Strategy: See endpoint #2
 
Population-Level Summary: See endpoint #2
 
Endpoint: Incidence of PCR-adjusted parasitemia (thick smear/microscopy, after adjustment for parasitemia due to recrudescence as determined by genotyping using PCR techniques).
 
Population: see primary endpoint
 
Treatment: See primary endpoint
 
Intercurrent Event Strategy: See endpoint #2
 
Population-Level Summary: See endpoint #2
	4
To evaluate the parasite clearance time in adults and adolescents with asymptomatic P. falciparum malaria treated with different doses of M5717 in combination with pyronaridine	
Endpoint: Parasite clearance time defined as time from dosing to the first negative (no parasites) blood film (microscopy)
 
Target Population: See primary endpoint
 
Treatment: See primary endpoint
 
Intercurrent Event Strategy:
 
 • Intake of rescue medication after study treatment and before negative blood smear: treatment policy strategy, i.e. treatment effect is estimated regardless of ICE • Intake of antibiotics or other prohibited medication that impacts treatment effect (e.g. drug with antimalarial activity) at the time or after the time of study treatment, but before first negative blood smear: Treatment policy strategy • Experience of any event that affects absorption (i.e. vomiting within the first 24 hours after dosing): Treatment policy strategy, i.e. treatment effect is estimated regardless of ICE • Death before negative blood smear: On-treatment strategy, i.e. time to parasite clearance is censored at the time of death 
Population-level Summary: Median parasite clearance time as estimated by Kaplan-Meier method for each dose of M5717
	5
To evaluate the safety and tolerability of different doses of M5717 in combination with pyronaridine in adults and adolescents with asymptomatic P. falciparum malaria	Endpoint: Incidence, severity, and seriousness of TEAEs, treatment-emergent study intervention related AEs, as per CTCAE v 5.0	6

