9.2 Investigational Medical Product (IMP)

The IMP is the combination of M5717 and pyronaridine (given at 2 different dose levels according to body weight (540 mg for participants between 45 and 65 kg and 720 mg for participants with a body weight above 65 kg)) and Malarone. It has to be noted, though, that no effect of Malarone is investigated with the trial; it is only used to initially clear all parasites from the participants in order to monitor the natural incidence of reinfections (since after parasite clearance participants are left untreated).

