- **Death due to malaria or other reasons:** filter SAEs programmatically for fatal events with outcome "death" and by medical/safety review. Death cases for which the primary reason is ticked as "progressive disease and/or disease-related condition" qualify as death due to malaria. A composite variable strategy is applied if the death was due to malaria (i.e. a parasitemia event is considered at the time of death) and an on-treatment strategy is defined if death was due to other reasons (i.e. time to parasitemia is censored at the time of death)

The population-level summary is defined as the Hazard Ratios (HRs) for each dose of M5717 relative to the untreated participants in Cohort 4. HRs are estimated from a Cox Proportional Hazards Model with time to parasitemia included as the dependent variable and dose cohorts, site and sex included as independent factors, and baseline age, body weight and parasite density included as independent covariates. Participants will be censored in case of occurrence of an ICE as described above, at the last available visit in case of premature study discontinuation or at the end of study in case no parasitemia event was observed.

For the multivariable (primary) model, a table showing HRs together with 95% Wald CIs will be provided which will contain in addition estimates of coefficients, SEs and p-values (based on Likelihood Ratio Test) in order to assess whether the factors and covariates included into the model have a significant influence on the time to parasitemia. As additional information a table providing information on censoring frequency and occurrence of ICEs will be provided.

As part of descriptive analyses of the primary endpoint, which also covers the analysis of the second estimand (incidence of parasitemia), a table displaying number and percentages of

parasitemia events (estimated directly from the data) will be provided together with estimates of a Kaplan-Meier (KM) analysis. Median time of protection and 95% CI will be estimated using the KM method for each cohort. As a graphical illustration, a KM-figure will be provided showing time to parasitemia in days after parasite clearance.

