14.2.2 PCR-adjusted Parasitemia

For PCR-adjusted parasitemia (thick smear/microscopy, after adjustment for parasitemia due to new infections and due to recrudescence, respectively) the same analyses and outputs will be provided as for the primary estimand. For the derivation of the population-level summary the same ICEs and strategies are applied as for the primary estimand as described in Section 14.1.1.

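### For PCR-confirmed recrudescence (endpoint 3), the planned Cox hazard ratio against Cohort 4 compares cure with Malarone, not protection with natural infection, and may not be estimable

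*SAP*

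**What the plan says.** SAP 14.2.2 covers parasitemia "after adjustment for parasitemia due to new infections and due to recrudescence, respectively", that is, endpoints 3 and 4 together, and states that "the same analyses and outputs will be provided as for the primary estimand". It also carries over the primary intercurrent-event rules.

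The primary analysis is in SAP 14.1.1: "The population-level summary is defined as the Hazard Ratios (HRs) for each dose of M5717 relative to the untreated participants in Cohort 4". The model is set out there too: "HRs are estimated from a Cox Proportional Hazards Model with time to parasitemia included as the dependent variable and dose cohorts, site and sex", with baseline age, body weight and parasite density as covariates. SAP 9.1 labels Cohort 4 *Natural Infection* in the outputs.

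SAP Section 5 defines endpoint 3 as parasitemia "after adjustment for parasitemia due to new infections as determined by genotyping using PCR techniques", which leaves recrudescence. Its summary is given as "Population-Level Summary: See endpoint #2", and endpoint 2 specifies "Proportion of participants with parasitemia using Kaplan-Meier estimates for each dose of M5717 and for Cohort 4". Protocol Section 3 makes the same cross-reference, but protocol 9.4.1.2 says that the PCR-adjusted endpoints take estimand attributes similar to those of the primary endpoint, whose summary is an HR.

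On the role of the comparator, SAP 9.2 says that "no effect of Malarone is investigated with the trial; it is only used to initially clear all parasites from the participants". Protocol 4.2 describes Cohort 4 as a simulated group of uninfected people who soon have no drug protection.

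**The concern.** The reference group changes meaning between the two PCR-adjusted endpoints. For new infections, Cohort 4 measures what the objective asks for: the natural incidence of infection. For recrudescence, it measures whether three days of Malarone cured the infection present at enrolment. An HR against it is a comparison of cure with an active regimen, which SAP 9.2 says the trial does not investigate, printed under a natural-infection label.

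The better Malarone does what it is there to do, the fewer events the reference has and the less the HR can be estimated. A reader of the output table could then see a non-estimable value or a finite value of either sign, and none of these would speak to protection compared with natural incidence. The study is meant to inform the dose regimen for later phases (protocol 4.2), so an output that can mislead in either direction is better removed before the analysis.

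**Working it through.** **The plan's own figure.** Protocol 9.2 gives 80% power for any parasitemia, highest dose v Cohort 4, with 21 events and HR 0.29. Schoenfeld, two-sided 0.05: √21 × |ln 0.29| / 2 − 1.96 = 4.583 × 1.238 / 2 − 1.96 = 0.877, so power is 0.81. This reproduces, but it concerns any parasitemia. No figure is given for recrudescence.

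**Inputs.** 45 evaluable participants per cohort (protocol 9.2). Recrudescence rates are not in the documents; I assume 0 to 5% in Cohort 4, and 1, 2 or 5% in a dose cohort.

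**Step 1: no event in the reference.** P(0 of 45) = (1 − r)^45:
- r = 0: 1.00
- r = 1%: 0.99^45 = 0.64
- r = 2%: 0.98^45 = 0.40
- r = 5%: 0.95^45 = 0.10

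**Step 2: what one dose HR then looks like.** Independent binomial counts, 45 per cohort. Finite values are classed by event counts.

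| Cohort 4 rate | Dose-cohort rate | HR infinite | HR zero | Undefined (0 v 0) | Finite, >1 | Finite, ≤1 |
|---|---|---|---|---|---|---|
| 0% | 5% | 0.90 | 0 | 0.10 | 0 | 0 |
| 1% | 5% | 0.57 | 0.04 | 0.06 | 0.22 | 0.11 |
| 2% | 5% | 0.36 | 0.06 | 0.04 | 0.32 | 0.22 |
| 5% | 5% | 0.09 | 0.09 | 0.01 | 0.31 | 0.50 |
| 2% | 2% | 0.24 | 0.24 | 0.16 | 0.10 | 0.26 |

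At 2% in both cohorts, the chance of no usable HR is 0.24 + 0.24 + 0.16 = 0.64.

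**Step 3: precision when the HR is finite.** With 3 events in a dose cohort and 1 in Cohort 4, and equal follow-up, the ratio is 3. SE(log) = √(1/1 + 1/3) = 1.155, and exp(1.099 ± 1.96 × 1.155) = 0.31 to 28.8. Unadjusted Cox fits to illustrative data with new infections censored give 2.6 (0.27 to 25) for 3 v 1, and 0.44 (0.04 to 4.9) for 1 v 2. The planned model asks more of such counts: 3 dose terms, sex, age, weight and density make 7 parameters before any site terms.

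**Step 4: the rescue rule.** Under SAP 14.1.1 rescue intake is treated as a positive smear, and SAP 14.2.2 keeps that rule. Protocol 6.8.1 leaves asymptomatic parasitemia to national guidelines or medical judgment, so a new infection may be followed by rescue. The SAP does not say whether a PCR-confirmed new infection is censored before the rescue rule applies. As an extreme case, take the protocol's 37% parasitemia in Cohort 4: 45 × 0.37 ≈ 17. If all 17 were new infections, rescued and counted, against an assumed 3 events in a dose cohort, an illustrative Cox fit gives HR 0.13 (0.04 to 0.46). That apparent benefit on recrudescence would come only from how events are counted.

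**The case against.** Four points on the other side carry weight.

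- **The HR has a protocol basis.** A reader might infer that the Cox step has no estimand behind it. Protocol 9.4.1.2 does extend primary-like attributes to the PCR-adjusted endpoints, so the accurate statement is that the protocol conflicts with itself and with SAP Section 5. Protocol Table 4 is also redacted after endpoint 2, so further text may exist there.
- **The outcome is not fixed.** A reader might infer that the HRs must be infinite or look worse than natural infection, or that all three diverge together. The table shows that zero, undefined and finite values below 1 also occur. With no Cohort 4 event, all three HRs are infinite only if every dose cohort has an event: (1 − (1 − r)^45)³ is about 5%, 21% and 73% at dose-cohort rates of 1, 2 and 5%.
- **Near zero is the design intent, not a documented rate.** Every probability above rests on an assumed failure rate. Nor can the protocol's 13% parasitemia be used to project recrudescence across doses, because it is assumed for the highest dose only and covers any parasitemia.
- **The better output is already planned.** The repeated SAP 14.1.1 outputs include event counts and Kaplan-Meier estimates by cohort, and protocol 9.1 makes all analyses descriptive. No decision rule in the readable text uses this HR.

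These points lower the priority. They do not make Cohort 4 a natural-infection reference for recrudescence, and the readable text has no rule for sparse or zero events.

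**Conclusion.** The point holds in a limited form. As written, SAP 14.2.2 produces an HR for recrudescence against a group whose true events can only be Malarone cure failures or PCR misclassification. That HR cannot address the stated objective, whatever value it takes. At assumed Malarone failure rates of 0 to 2%, the chance that the reference has no event is 100% down to 40%; at 5% it is 10%. Finite results would carry intervals spanning about two orders of magnitude, and the unspecified handling of rescue could move the HR in the opposite direction. The same HR for endpoint 4 is sound and should stay. Because the analyses are descriptive and Kaplan-Meier outputs are already planned, this is a moderate-to-low priority correction.

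**What to change.** - In SAP 14.2.2, limit the Cox HR against Cohort 4 to endpoint 4.
- For endpoint 3, report counts and Kaplan-Meier proportions by cohort with 95% CIs, as SAP Section 5 defines. Label the Cohort 4 figure as recrudescence after Malarone.
- State that in the endpoint 3 analysis a PCR-confirmed new infection is censored at detection, and that rescue given for it is not counted as a recrudescence event. Without this, the by-cohort proportions would be contaminated in the same way as the HR.
- Align protocol 9.4.1.2 with SAP Section 5.

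The cost is a few sentences, one fewer model and no new data. The small loss is an adjusted HR for recrudescence.

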14.2.3 Parasite Clearance Time

For estimating parasite clearance time (in hours), which is the time from dosing (first dose in the Malarone treatment cohort) to the first negative blood film (parasite count of 0 on microscopy), followed at least by 1 subsequent visit with a negative blood film. Patients should not be considered for analysis if they did not have parasites >0 at any timepoint. The same ICEs as defined in Section 5 will be considered. The median parasite clearance time will be estimated by use of Kaplan-Meier method for each cohort. Participants will be censored in case of occurrence of an ICE if the ICE occurred before the first negative blood film, at the last available visit in case of premature study discontinuation before the first negative blood film or at the end of study in case no parasite clearance event was observed.

15 Safety Analyses

This section includes specifications for summarizing safety endpoints that are common across clinical studies such as adverse events, laboratory tests and vital signs.

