Data and Safety Monitoring /Other Committee: Yes

A Data Monitoring Committee (DMC) will evaluate the safety data of participants, if judged to be necessary by the Sponsor clinical team.

1.2

Schema

Figure 1

Schematic for the Proof-of-Concept Phase 2a Study: M5717 plus
Pyronaridine for Chemoprevention

a Data will be obtained from a clinical study sponsored by Shin Poong Pharmaceuticals Co. Ltd. (ClinicalTrials.gov Identifier: NCT03814616) and published by Dabira ED, Hachizovu S, Conteh B, et al. Efficacy, Safety and Tolerability of Pyronaridine-artesunate in Asymptomatic Malaria-infected Individuals: a Randomized Controlled Trial. Clin Infect Dis. 2022;74(2):180-88. Data of the 1-day treatment arm of this clinical study will be used as Cohort 5

Note: A Data Monitoring Committee will evaluate the safety data of participants, if judged to be necessary by the Sponsor clinical team

1.3

Schedule of Activities

Table 1 Schedule of Activities – Cohorts 1 to 4

Assessments & Procedures	Outpatient	Outpatient/ Inpatient ^a		Outpatient					Notes
Visit Number	Prescreening	Scr + Visit 1 ^a	Visit 2 ^a	Visit 3	Visit 4	Visits 5 to 12	Visit 13	Unscheduled Visit	^a Visit 1 and 2: Participants randomized to Cohorts 1 to 3 will remain in hospital or stay in the vicinity of the sites for 24 hours for PK sampling and assessment of parasitemia (see Table 2). Participants randomized to Cohort 4, will visit the clinic on Days 1, 2, and 3 for dosing in an outpatient setting
Timepoint	Prescreening	Day 1	Day 2	Day 3	Day 4	Week 2 to 9 (weekly visits starting at Day 8)	EOS (last visit) Week 10, Day 64 ^b	Can be required due to AEs, and AESIs; follow-up of AEs and AESIs	
Visit Window						± 1 day	± 2 days		
Prescreening consent	X								
Informed consent		X							
CCI [REDACTED]		[REDACTED]						[REDACTED]	[REDACTED].
Informed consent DMFA substudy		X							Additional informed consent for the DMFA substudy (optional, see Appendix 2).
Malaria diagnostics	X								For asymptomatic malaria (RDT as per standard of care).

Assessments & Procedures	Outpatient	Outpatient/ Inpatient ^a		Outpatient					Notes	

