Visit Number	Prescreening	Scr + Visit 1 ^a	Visit 2 ^a	Visit 3	Visit 4	Visits 5 to 12	Visit 13	Unscheduled Visit	
^a Visit 1 and 2: Participants randomized to Cohorts 1 to 3 will remain in hospital or stay in the vicinity of the sites for 24 hours for PK sampling and assessment of parasitemia (see Table 2).
 
Participants randomized to Cohort 4, will visit the clinic on Days 1, 2, and 3 for dosing in an outpatient setting
	
Timepoint	Prescreening	Day 1	Day 2	Day 3	Day 4	Week 2 to 9 (weekly visits starting at Day 8)	EOS (last visit) Week 10, Day 64 ^b	Can be required due to AEs, and AESIs; follow-up of AEs and AESIs	
^b Day 64 or day of completion or premature discontinuation.
 
Participants will remain in the study until parasitemia or until Day 64, whichever comes first.
 
All EOS evaluations will be completed before providing antimalarial rescue treatment if required.
	
Blood films (microscopy)		X	X	X	X	X	X		
Thick and thin blood films will be collected at Visit 1 (predose) to confirm eligibility and at all visits.
 
Cohorts 1 to 3: The exact timepoints on Days 1 to 2 are provided in Table 2.
 
Cohort 4: Blood films should be examined at Screening, predose on Day 1, Day 2, and Day 3.
 
Blood sampling for parasitemia will be done simultaneously with PK.
	
Inclusion/ exclusion criteria		X								
COVID-19 antigen test		X							
The test will be conducted at Visit 1. Additional COVID-19 tests may be conducted as needed.
	
Demographic and medical history		X								
Randomization		X								

Assessments & Procedures	Outpatient	Outpatient/Inpatient ^a		Outpatient					Notes	
Visit Number	Prescreening	Scr + Visit 1 ^a	Visit 2 ^a	Visit 3	Visit 4	Visits 5 to 12	Visit 13	Unscheduled Visit	
^a Visit 1 and 2: Participants randomized to Cohorts 1 to 3 will remain in hospital or stay in the vicinity of the sites for 24 hours for PK sampling and assessment of parasitemia (see Table 2).
 
Participants randomized to Cohort 4, will visit the clinic on Days 1, 2, and 3 for dosing in an outpatient setting
	

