Table 2 Pharmacokinetics and Blood Films: Sampling Timepoints on Days 1 and 2 – Cohorts 1 to 3

Assessment									Notes
Visit	1							2	
Day	1							2	For subsequent PK blood sampling for M5717 and pyronaridine refer to Table 1
Window		± 5min	± 10 min	± 20 min	± 30 min	± 30 min	± 60 min	± 120 min	
Hours after M5717 + pyronaridine dose	Pre	1h	2h	4h	6h	8h	12h	24h	
PK blood sampling for M5717	X	X	X	X	X	X	X	X	Not applicable for Cohort 4.
PK blood sampling for pyronaridine	X	X	X	X	X	X	X	X	Not applicable for Cohort 4.
Blood films (microscopy)	X	X			X		X	X	Not applicable for Cohort 4.

PK = pharmacokinetic(s).

2 Introduction

M5717 is a first-in-class NCE targeting the *Plasmodium* cytosolic protein synthesis “Elongation Factor 2” for the treatment and prevention of malaria due to the activity in the liver and blood stage of the parasite life cycle.

Pyronaridine tetraphosphate is an antimalarial drug marketed in combination with artesunate as Pyramax for which the CHMP adopted a positive scientific opinion in accordance with Art 58 of (EC) Regulation 726/2004 on 16 February 2012. Pyronaridine is a drug that interferes with the digestive system of *P. falciparum* and *P. berghei* and inhibits the production of complexes with β -hematin to enhance hematin-induced human blood cell lysis (Croft 2012).

M5717 and pyronaridine are intended to be developed as a fixed-dose combination for either the treatment of acute uncomplicated malaria or for the prevention of symptomatic malaria in populations living in endemic areas. The initial step of the clinical development plan of the combination is to generate initial safety, efficacy, and exposure data in symptomatic malaria patients and asymptomatic, malaria-infected individuals through the conduct of 2 Phase 2a PoC studies (CAPTURE-1 and CAPTURE-2) to prioritize the final indication for Phase 2b and Phase 3.

There is a clear need to accelerate the development of dedicated drug combinations for malaria prevention. A reduction of >50% of malaria cases was observed in regions where malaria preventive treatments were systematically applied (Cairns 2012) leading to a significant reduction in mortality in the population. WHO has recently published new treatment policies to reinforce the use of chemoprevention (WHO Guidelines for Malaria, 2022), which combined with the increasing development of resistance against the 2 main standards of care, highlights the need for dedicated new therapies.

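### Parasite clearance time is summarised for Cohort 4 beside Cohorts 1–3 although only Cohorts 1–3 have blood films in the first 12 hours, so the medians are not comparable if clearance is that early

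*SAP*

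**What the plan says.** SAP 14.2.3 measures clearance in hours, as "time from dosing (first dose in the Malarone treatment cohort) to the first negative blood film", with the condition that this film is "followed at least by 1 subsequent visit with a negative blood film". It then plans the summary: "The median parasite clearance time will be estimated by use of Kaplan-Meier method for each cohort". The start time set for Malarone shows that Cohort 4 is meant to be included. SAP 9.1 and 9.3 present tables and figures by treatment group, with the natural infection cohort as one of the groups.

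SAP Section 5 (estimand 5) gives a narrower summary: "Median parasite clearance time as estimated by Kaplan-Meier method for each dose of M5717". Protocol Section 3 agrees with it. The treatment attribute of that estimand refers back to the primary estimand, which lists Cohort 4, but both the objective and the summary measure name only the M5717 doses.

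The films are scheduled in Protocol Section 1.3. Table 2 is titled "Pharmacokinetics and Blood Films: Sampling Timepoints on Days 1 and 2 – Cohorts 1 to 3". Its time axis is "Hours after M5717 + pyronaridine dose", its film row is marked at predose, 1, 6, 12 and 24 h, and that row is noted as not applicable to Cohort 4. For Cohort 4, Table 1 says: "Cohort 4: Blood films should be examined at Screening, predose on Day 1, Day 2, and Day 3". Table 1 also says: "Participants randomized to Cohort 4, will visit the clinic on Days 1, 2, and 3 for dosing in an outpatient setting". From Day 3 on, all cohorts have films at the same visits.

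**The concern.** A clearance time read as the first negative film is the true time rounded up to the next scheduled film, and Kaplan-Meier then treats that film time as exact. In Cohorts 1–3 the rounding can stop at 1, 6 or 12 h. In Cohort 4 it cannot stop before about 24 h, whatever the drug does. If clearance is early, a table of medians in hours by cohort, or a set of clearance curves, would show M5717 plus pyronaridine clearing faster than Malarone even if the two clear at the same rate. The error can run only in favour of the experimental cohorts.

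Two rules might have removed the difference, but neither does. The confirmation rule requires a negative film at a later visit but leaves the event at the first negative film, so a 6 h or 12 h negative confirmed at Visit 2 keeps its early time. SAP 9.3 generally keeps unscheduled measurements out of the analyses, so extra early films in Cohort 4 would not enter.

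**Working it through.** The documents state no clearance figure, so there is nothing to reproduce.

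**Inputs.** Post-dose films for Cohorts 1–3 at 1, 6, 12, 24, 48, 72 h, then weekly (Protocol Section 1.3, Tables 1 and 2). Post-dose films for Cohort 4 at 24, 48, 72 h, then weekly (Table 1, reading predose Day 2 as 24 h). 45 participants per cohort (Protocol 9.2). The true clearance time is an assumption, varied below.

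**Step 1: one participant.** Scored time = first scheduled film at or after true clearance. Difference = Cohort 4 score minus Cohorts 1–3 score.

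| True clearance after dosing | Cohorts 1–3 | Cohort 4 | Difference |
|---|---|---|---|
| up to 1 h | 1 h | 24 h | 24 − 1 = 23 h |
| after 1, up to 6 h | 6 h | 24 h | 24 − 6 = 18 h |
| after 6, up to 12 h | 12 h | 24 h | 24 − 12 = 12 h |
| after 12, up to 24 h | 24 h | 24 h | 0 h |
| after 24, up to 48 h | 48 h | 48 h | 0 h |

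Table 2 allows ±60 min at 12 h and ±120 min at 24 h. If Cohort 4 is assumed to have the same ±120 min, the 12 h difference runs from 22 − 13 = 9 h to 26 − 11 = 15 h.

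**Step 2: the medians.** Rounding up preserves order, so without censoring the scored median is the true median rounded up to the next film. In a large sample the gap in medians therefore follows the table: 18 h for a true median after 1 and up to 6 h, 12 h after 6 and up to 12 h, and 0 h beyond. With 45 participants, chance blurs the steps near 6 and 12 h. The blur was simulated with the same true distribution in both groups: lognormal, SD of log time 0.5, 45 per group, 4,000 runs. The table gives the average of the scored medians.

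| Assumed true median | Cohorts 1–3 | Cohort 4 | Gap |
|---|---|---|---|
| 4 h | 6.0 h | 24.0 h | 18.0 h |
| 6 h | 9.0 h | 24.0 h | 15.0 h |
| 8 h | 12.0 h | 24.0 h | 12.0 h |
| 10 h | 12.3 h | 24.0 h | 11.7 h |
| 12 h | 17.9 h | 24.0 h | 6.1 h |
| 13 h | 21.6 h | 24.0 h | 2.4 h |
| 14 h | 23.4 h | 24.0 h | 0.6 h |
| 16 h | 24.0 h | 24.0 h | 0.0 h |

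For true medians of 20 to 48 h the gap is at most 0.2 h in either direction. The 6 h row is an average over a knife edge: in any one trial the scored median in Cohorts 1–3 is 6 h or 12 h, so the gap is 18 h or 12 h.

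**Step 3: after the change.** With every cohort read on the shared films only, the difference in medians is at most 0.2 h, which is simulation error, at every true median tried (4 to 48 h).

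**The case against.** The strongest reply is that the trial does not set out to compare clearance on M5717 with clearance on Malarone. The objective and the summary measure of estimand 5 cover the M5717 doses. SAP 9.2 says that the trial does not study an effect of Malarone, which serves only to clear parasites at the start. Protocol 9.1 makes all analyses descriptive. No test, hazard ratio or decision rule sets clearance time against Cohort 4. All of this stands and limits the point to how a secondary display would be read. It does not remove the point, because SAP 14.2.3 still asks for the Cohort 4 median and so differs from Section 5.

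A reader might infer more than the documents support in three ways:

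- **That the table will show faster clearance on M5717.** The documents give no expected clearance time. The films at 1, 6 and 12 h show that early clearance was allowed for, not that it is expected.
- **That the artefact covers all of the first day.** It stops at 12 h. Anyone who clears between 12 and 24 h is scored 24 h in every cohort.
- **That the primary analysis is compromised.** Its clock also starts at the first negative smear (SAP 14.1.1), but it counts days. The shift in start is at most about 1 day in roughly 63, which is minor.

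**Conclusion.** The point holds as a reporting defect of minor priority. As written, SAP 14.2.3 gives medians that are not comparable between Cohort 4 and Cohorts 1–3, and any distortion favours M5717. The individual differences of 23, 18, 12 and 0 h follow from the schedules alone, given that predose on Day 2 means about 24 h. The size of the gap in medians depends on a true clearance time that the documents do not give. It is about 12 h or more for true medians up to about 10 h, falls through about 6 h at a true median of 12 h, and is negligible from about 14–16 h. The lognormal shape and its spread are assumptions; they affect mainly how sharply the gap falls around 12 h.

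Separately from any bias, SAP 14.2.3 and SAP Section 5 disagree on which groups are summarised and should be reconciled.

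**What to change.** In SAP 14.2.3, restrict the Kaplan-Meier median based on all films to Cohorts 1–3, which matches SAP Section 5 and Protocol Section 3. If any table or figure shows Cohort 4 beside them, derive clearance in all cohorts from the shared films only (Days 2, 3 and 4, then weekly) and footnote the differing schedules.

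An interval-censored estimate is not a good substitute. If most of Cohort 4 is negative at the first post-dose film, their clearance lies somewhere between 0 and about 24 h, and a nonparametric median is not identified inside that interval.

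The cost is a change of SAP wording and, if Cohort 4 is displayed, one extra derived variable. Trial conduct does not change. The drawback is that the shared-film version is coarser for Cohorts 1–3, so it should be added to their all-film median and not replace it.
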